9.4. PHYSICAL EXAMINATION

A complete physical examination will be performed at Screening Visit (Visit 1), Visit 3 (Randomization) prior to first dose of study medication, and at the Visit 12 (End of

Study/Early Termination). An abbreviated physical exam is performed at Visit 6 (Day 15), Visit 8 (Day 43), and Visit 10 (Day 71). A complete or abbreviated physical exam may be performed at the Cardiac follow-up visit for subjects who do not enter the open-label extension study if clinically warranted. Clinically significant findings at screening will be reported on the medical history page. New clinically significant findings starting with after the first dose in Part 1 will be reported as adverse events.

A summary of subjects with clinically significant physical examination findings at each visit will be provided for the T+M period.

All physical examination results will be presented in a subject data listing.

9.5. NEUROLOGIC EXAMINATION

In Part 1, a complete neurological examination will be performed at Visit 1 (Screening) and Visit 12 (End of Study / Early Termination). An abbreviated neurological examination will be performed at Visit 3 (Randomization) and at Visit 6 (Day 15), Visit 8 (Day 43), and Visit 10 (Day 71). Clinically significant findings at screening will be reported on the medical history page. New clinically significant findings starting with after the first dose in Part 1 will be reported as adverse events.

A summary of subjects with clinically significant neurologic examination findings at each visit will be provided for the T+M period.

All neurological examination results will be presented in a subject data listing.

9.6. VITAL SIGNS, WEIGHT, AND BMI

Vital signs data will be documented for subjects during study at screening visit (Visit 1), Visit 3 (Randomization) prior to first dose of study medication, at the end of the titration period at Visit 6 (Day 15), during the maintenance period at Visit 8 (Day 43) and Visit 10 (Day 71), and at Visit 12 (End of Study / Early Termination). The measurements will include blood pressure, heart rate, temperature, respiratory rate, weight, and BMI.

For each vital sign, observed values and change from baseline to each on-study evaluation will be summarized.

For weight and BMI, the occurrence of at least a $\geq 7\%$ gain/reduction or $\geq 10\%$ gain/reduction from baseline will be summarized by visit and at any time during the T+M treatment period. For subjects with an occurrence of a $\geq 7\%$ reduction in weight or BMI, the number who achieved a recovery to their baseline weight, and the duration of time to recovery, will be summarized, and whether that recovery was achieved as a result of a reduction or withdrawal of the subject's study medication. Recovery will be defined as achieving a weight after the >= 7% reduction, that is at least 99% of the baseline weight and having a weight at Visit 12 that is at least 99% of the baseline weight. The number of days until weight recovery will be determined using the date of the first date where the weight loss was observed and the first date where the subject's weight had recovered to, and maintained for the duration of the study period, at least 99% of the baseline weight.

For subjects with at least a 7% reduction in body weight, a spagnetti plot of showing the subject's weight values by study day will be presented by actual treatment group.

Vital signs, Weight and BMI data will be presented in a data listing.

For each subject with a clinically meaningful abnormality in vital signs, (to be supplied by Zogenix International), a table will be produced organized by parameter that lists each subject, age, sex, day of most abnormal value, the most abnormal value, and the reference range, and first date of a normal value (occurring after the abnormality).

A listing of subjects with at least a 7% reduction in weight/BMI and clinically meaningful abnormal values will be created.

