Taper/Transition Period	The Taper/Transition period consists of 2 weeks starting from end of study/early termination visit (Visit 12) + 1 day through Visit 13 (Taper) or Visit 15 (Transition to Part 2). For subjects who are not entering into the Part 2 of the study, subjects will gradually be tapered off of study medication. For subjects who are entering Part 2, subjects will enter the transition phase where all subjects will be on a dose of 0.2	
	mg/kg/day at the end of this phase.	

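### SAP 9.6: a 7% weight loss first seen at Visit 12/ET cannot count as recovered, because no later weight is listed, yet the subject stays in the recovery summary

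*SAP*

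**What the plan says.** Section 9.6 schedules weight at Visits 1, 3, 6, 8, 10 and 12, where Visit 12 is the end-of-study or early-termination visit. It tabulates gains and losses of at least 7% and at least 10%, by visit and at any time in T+M. Section 6.7 runs T+M through Visit 12 and makes Visit 12 the early-termination visit for those who leave early.

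For subjects with a loss of at least 7%, Section 9.6 then reports how many recovered and how long it took. The definition has two parts, and both must be met. One concerns the final visit: "having a weight at Visit 12 that is at least 99% of the baseline weight". The other asks for regain at some point following the loss, to the same 99% threshold. Time to recovery ends on the first date at which weight had "recovered to, and maintained for the duration of the study period, at least 99% of the baseline weight". The same paragraph will also report "whether that recovery was achieved as a result of a reduction or withdrawal of the subject's study medication".

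On stopping drug, Section 6.7 states: "The Taper/Transition period consists of 2 weeks starting from end of study/early termination visit (Visit 12) + 1 day". The SAP addendum lists the weight summary (Table 14.4.1.2.2.1) without modification.

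**The concern.** The summarised group includes everyone who loses 7% at any point up to and including Visit 12, but the definition can be met only by someone weighed again afterwards. No rule marks a loss first seen at Visit 12/ET as not assessable, or censors it in the time to recovery. A reader of the table cannot tell a subject who was followed and did not regain weight from one who was never weighed again.

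Body weight and BMI are listed safety endpoints (Section 5.4), and this is the display that speaks to reversibility. If one arm loses weight later, or has more early terminations, more of its subjects fall into the group that cannot recover, and the comparison between arms is distorted.

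The withdrawal attribution has a related problem. On the planned schedule, dosing continues to Visit 12/ET and is stepped down afterwards, so weight regained off drug comes too late to enter the definition.

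**Working it through.** The plan gives no figure to reproduce, so the first check is one of logic.

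**Can a loss first seen at Visit 12 count as recovered?** The loss means a Visit 12 weight of at most 100% − 7% = 93% of baseline. Recovery needs at least 99% at the same visit. Both cannot hold.

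**All possible patterns.** Code each on-treatment weight (Visits 6, 8, 10, 12) as loss (≤93%), between, or recovered (≥99%). There are 3⁴ = 81 patterns, of which 81 − 2⁴ = 65 contain a loss. Applying the Section 9.6 rule, with and without its Visit 12 condition:

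| First loss at | Patterns | Recovered, rule as written | Recovered, Visit 12 condition removed |
|---|---|---|---|
| Visit 6 | 27 | 9 | 19 |
| Visit 8 | 18 | 6 | 10 |
| Visit 10 | 12 | 4 | 4 |
| Visit 12 | 8 | 0 | 0 |

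These are pattern counts, not expected patients. They show that the Visit 12 first-loss group is stuck at zero under either rule. The obstacle is the lack of a later listed weight; removing the Visit 12 condition would only loosen the rule for earlier losses.

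**How many subjects might be affected?** The SAP gives no weight trajectory, so every input here is an assumption: percentage change by Visit 12 with mean 0 to −4% and SD 4–5%, visit-to-visit noise SD 1–1.5%, weights at Days 15, 43, 71 and 99. Share of all subjects with a loss of at least 7% who first show it at Visit 12:

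- Steady linear drift to Visit 12: 50% to 77%.
- Loss slowing with a half-life of 2 to 6 weeks (SD 4.5%, noise 1.25%): 12% to 41%.
- Early loss then plateau (half-life 14–21 days, or flat from Day 43): 6% to 30%.

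If a share p is first seen at Visit 12, and all earlier losers have a later weight, then

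recovered share as counted = (1 − p) × recovered share among assessable subjects.

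The multiplier is 1 − 0.06 = 0.94 at one end and 1 − 0.77 = 0.23 at the other.

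**Withdrawal attribution.** Tables 2 and 3 (Section 4.4) and Section 6.7 place taper or transition after Visit 12 or early termination. Weight regained in that period cannot change the Visit 12 value. Section 6.7 itself extends the safety period to the end of Taper/Transition, so the recovery rule stops short of the plan's own safety window.

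**The case against.** Several points on the other side stand.

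- The Visit 12 condition does a sensible job. It requires recovery to be sustained and matches the time-to-recovery rule. What happens to late losses is ordinary end-of-window censoring, and the table above shows the condition is not its cause.
- A reader might infer that anyone who recovers after stopping drug can never count. The document does not support that. Section 9.3.1 lists stopping treatment separately from leaving the study, and Section 6.7 allows for no taper. A subject off drug before the Visit 12/ET weight, and at 99% or more there, meets both conditions. Recovery after a dose reduction before Visit 12 is not shown to be affected.
- A reader might also want a single figure for the bias. None is available. Linear drift puts the greatest loss at the last visit by construction, and other shapes give far smaller shares. Linear drift also yields almost no true recovery, so pairing its share with an assumed recovery rate would join two incompatible models.
- Section 9.6 promises a number recovered and writes no percentage. Its by-visit summary, spaghetti plot and listing let a careful reader see who first crossed 7% at Visit 12.

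The other displays do not repair the recovery summary, which still gives one undivided group. It is also possible that weights after Visit 12 exist: the weight row of the assessment schedule (Table 4) is not legible in the text at hand, and Part 2 methods are in a separate SAP (Section 2.2).

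**Conclusion.** The point holds in a limited form. From the wording alone, losses of 7% or more first seen at Visit 12/ET are in the summarised group and cannot be counted as recovered. Recovery is understated as a result, and unevenly if arms differ in timing of loss or early stopping. The size is not known; 6% to 77% of subjects with such a loss is the range under the assumed trajectories, and that width means the affected group should be reported, not guessed.

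Recovery after withdrawal is largely, not wholly, uncapturable on the planned schedule. This part rests on Section 9.6 giving the full list of weights used; a confirmed later weight source would change it.

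The display is descriptive. No hypothesis test, sample size or error rate depends on it.

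**What to change.** 1. Keep the Visit 12 condition, so that recovery means sustained recovery.
2. Summarise recovery and time to recovery among subjects whose first loss of at least 7% precedes Visit 12/ET and who have a later weight.
3. Add a row, by arm, for losses first seen at Visit 12/ET, labelled as not evaluable for recovery.
4. For the withdrawal attribution, either name an existing source of weights after Visit 12, if the sponsor confirms one, or drop that display from Part 1 or move it to the Part 2 SAP.

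The cost is a change of SAP wording, one extra table row and a smaller denominator for recovery. Items 1 to 3 need no new measurements; item 4 depends on what the sponsor confirms.

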9.7. ELECTROCARDIOGRAM

Analysis of Echocardiograms will be included in a separate report from ERT (formerly Biomedical Systems).

9.8. DOPPLER ECHOCARDIOGRAPHY

Results of ECHOs will be presented in a separate report from ERT (formerly Biomedical Systems).

9.9. TANNER STAGING

In Part 1, Tanner Staging will be assessed for subjects > 7 to 18 years old during the study at Visit 3 (Randomization) and Visit 12 (End of study / Early Termination).

Conceptually, pubertal maturation can be described in terms of sequence, timing, and tempo. Puberty consists of a series of predictable events, and the sequence of changes in secondary sexual characteristics has been categorized by several groups. The onset and progress of pubertal changes will be recorded on a 5-point scale for boys and girls separately. Boys are rated for genital development and pubic hair growth through stage I to stage V. Girls are rated for breast development and pubic hair growth through stage I to stage V.

The number and percentage of subjects in each Tanner Stage will be presented for all visits by treatment group separately for boys and girls overall and broken out for the following age groups:

- > 7 years to ≤11 years,
- > 11 years to ≤ 15 years,
- > 15 years to \leq 18 years.

All Tanner staging data will be presented in the subject data listing.

9.10. LABORATORY PARAMETERS

Laboratory safety parameters will be analyzed by a central laboratory using standard validated methods.

All laboratory safety data will be collected as per the schedule of assessments given in Table 4.

The following continuous laboratory parameters will be analyzed:

- Hematology: hemoglobin, hematocrit, erythrocytes, erythrocyte mean corpuscular volume, leukocytes, neutrophils, lymphocytes, monocytes, eosinophils, basophils and platelets
- Blood Biochemistry: albumin (ALB), alkaline phosphatase (AP), alanine aminotransferase (ALT; SGPT), aspartate aminotransferase (AST; SGOT), blood urea nitrogen (BUN), calcium (Ca), carbon dioxide (CO2), chloride (Cl), creatinine, creatine kinase, gamma-glutamyl transferase (GGT), globulin, glucose, lactate dehydrogenase (LDH), phosphorus, potassium (K), sodium (Na) thyroid function, thyroid stimulating hormone (TSH), total bilirubin, direct bilirubin, total cholesterol, total protein, triglycerides, uric acid.
- Tests of growth and precocious puberty: Growth hormone (GH), insulin-like growth factor-1 (IGF-1, low sensitivity), prolactin, Luteinizing Hormone (LH), Follicle Stimulating Hormone (FSH), testosterone, estradiol
- Coagulation: Prothrombin time (PT), International normalized ratio (INR), activated partial thromboplastin time (PTT)
- Whole blood cannabidiol
- Urinalysis: analysis for pH, glucose, ketones, nitrite, protein, bilirubin, urobilinogen, leukocyte esterase, and occult blood. Microscopic analysis will be performed for blood, all cell types, and casts.
- Pregnancy test: Urine or serum pregnancy testing will be performed in female subjects of childbearing potential.
- Urine or serum THC panel

Observed continuous laboratory data will be descriptively summarized by type of laboratory test/parameter change from baseline.

Categorical laboratory parameters will be summarized by presenting the number and % of subjects by visit and by treatment arm.

For each laboratory parameter, shift tables will be created comparing the baseline status with the status at each post-baseline visit. Status will be classified as:

- below lower limit of normal and clinically significant
- below lower limit of normal,
- within normal limits,
- above upper limit of normal,
- above upper limit of normal and clinically significant.

Listings of the most extreme values for a subject recorded in Part 1 and Part 2 will be created for each parameter. These will show the lowest recorded value and the highest recorded value noted for the subject. A listing of subjects with markedly abnormal laboratory results will be provided, and additional explorations of the data may be conducted as warranted.

Additionally, summaries of abnormal lab results by parameter will be provided to investigate changes in platelet count and prolactin in detail. The summaries include:

- Subjects with decrease (≥25% from baseline) in Platelets count with normal platelet count at baseline
- Subjects with decrease (≥25% from baseline) in Platelets count relative to baseline (whether normal or abnormal) platelet count
- Subjects with decrease (≥25% from baseline) in Platelets count with normal platelet count at baseline, by valproate use
- Subjects with decrease (≥25% from baseline) in Platelets count with normal platelet count at baseline, by presence/absence of infection event prior to 7 days of the lab assessment
- Subjects with increase (≥25% from baseline) in prolactin with normal baseline
- Subjects with increase (≥25% from baseline) in prolactin with normal baseline, and had seizure event within 48 hours prior to prolactin

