Table	14.3.4.3.4.2	Shift Tables for Laboratory Parameters in Part 1 - Urinalysis (Categorical Parameters) (Cohort B - Japan) Safety Population	
Table	14.3.4.4.1.1	Laboratory Parameters in Part 1 - Tests of Precocious Puberty and Thyroid Function: Summary Statistics (Cohort A - North America, Europe, Australia) - Safety Population	
Table	14.3.4.4.1.2	Laboratory Parameters in Part 1 - Tests of Precocious Puberty and Thyroid Function: Summary Statistics (Cohort B - Japan) - Safety Population	
Table	14.3.4.4.2.1	Shift Tables for Laboratory Parameters in Part 1 - Tests of Precocious Puberty and Thyroid Function (Cohort A - North America, Europe, Australia) - Safety Population	
Table	14.3.4.4.2.2	Shift Tables for Laboratory Parameters in Part 1 - Tests of Precocious Puberty and Thyroid Function (Cohort B - Japan) - Safety Population	
Table	14.3.4.5.1	Laboratory Parameters in Part 1 : Epilepsy Genotype Panel (Cohort A - North America, Europe, Australia) - Safety Population	
Table	14.3.4.5.2	Laboratory Parameters in Part 1 : Epilepsy Genotype Panel (Cohort B - Japan) - Safety Population	
	14.3.4.6.1.1	Number of Subjects with Decrease in Platelets Count During Part 1 with Normal Platelet Count at Baseline (Cohort A - North America, Europe, Australia) - Safety Population	
IMP	14.3.4.6.1.2	Number of Subjects with Decrease in Platelets Count During Part 1 with Normal Platelet Count at Baseline (Cohort B - Japan) - Safety Population	
	14.3.4.6.2.1	Number of Subjects with Decrease in Platelets Count During Part 1 Relative to Baseline (whether Normal or Abnormal) Platelet Count (Cohort A - North America, Europe, Australia) - Safety Population	
Table	14.3.4.6.2.2	Number of Subjects with Decrease in Platelets Count During Part 1 Relative to Baseline (whether Normal or	

on 2.0	Syneos Health #1009529A	
	Abnormal) Platelet Count (Cohort B - Japan) - Safety Population	ailation
14.3.4.6.3.1	Number of Subjects with Decrease in Platelets Count During Part 1 with Normal Platelet Count at Baseline by Valproate Use (Cohort A - North America, Europe, Australia)- Safety Population	notilati
14.3.4.6.3.2	Number of Subjects with Decrease in Platelets Count During Part 1 with Normal Platelet Count at Baseline by Valproate Use (Cohort B - Japan) - Safety Population	
14.3.4.6.4.1	Number of Subjects with Decrease in Platelets Count During Part 1 with Normal Platelet Count at Baseline by Presence/Absence of Infection Event (Cohort A- North America, Europe, Australia) - Safety Population	, o

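### Puberty-related hormones are summarised with both sexes and ages 2 to 35 pooled, and Tanner stage has no within-subject shift, so the planned summaries are poorly suited to detecting early or accelerated puberty

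*SAP*

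**What the plan says.** Hormones. Section 9.10 lists a panel that begins "Tests of growth and precocious puberty: Growth hormone (GH), insulin-like growth factor-1 (IGF-1, low sensitivity" and continues with prolactin, LH, FSH, testosterone and estradiol. The summary rule is the one used for every continuous analyte: "Observed continuous laboratory data will be descriptively summarized by type of laboratory test/parameter change from baseline". Section 9.10 also plans that "For each laboratory parameter, shift tables will be created comparing the baseline status with the status at each post-baseline visit", with status classed against lower and upper limits of normal and clinical significance. It does not say whether those limits depend on age or sex. The index in section 14 carries "Laboratory Parameters in Part 1 - Tests of Precocious Puberty and Thyroid Function: Summary Statistics" (Tables 14.3.4.4.1.1 and 14.3.4.4.1.2) and "Shift Tables for Laboratory Parameters in Part 1 - Tests of Precocious Puberty and Thyroid Function" (Tables 14.3.4.4.2.1 and 14.3.4.4.2.2), one per cohort, none with an age or sex split in its title. The 2021 addendum lists the same tables unchanged.

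Subgroups. The opening of the safety section reports results by treatment group unless noted otherwise. Section 6.9 restricts the age and sex subgroups to some efficacy analyses and to adverse events. The cardiovascular SAP (section 2.4) gives the population as male and female, 2 to 35 years.

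Tanner. Section 9.9 stages subjects older than 7 and up to 18 years at Visit 3 and Visit 12, and says that onset and progress are recorded. The output is the number and percentage at each stage for each visit, "by treatment group separately for boys and girls overall and broken out for the following age groups": over 7 to 11, over 11 to 15, and over 15 to 18 years. No shift or change-from-baseline table is planned.

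**The concern.** Precocious puberty is a question about young children, and the normal values of these hormones depend on age and sex. A single change-from-baseline summary per arm mixes young children, adolescents in mid-puberty and adults of both sexes. Its mean does not describe the subjects the panel was drawn for.

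This matters most at the youngest ages. Tanner staging starts only above 7 years, so from 2 to 7 the hormone panel is the only puberty-specific measure the SAP tabulates, and it is pooled with adult values.

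The SAP splits by age or sex in neighbouring places. Tanner counts are split by both and adverse events by each (section 9.3.2). The cardiovascular SAP splits QTcF by age and sex, and heart rate, QRS and PR by age. For Tanner stage, what is missing is a table showing how many children moved between stages. Section 9.10 plans shift tables for laboratory data, and section 14 lists one for the C-SSRS.

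**Working it through.** The SAP states no figure on this point, so there is none to reproduce. Three checks apply.

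**1. Is a split provided anywhere for the hormones?** Section 9.10 states none. Section 6.9 does not extend its subgroups to laboratory data. The table titles in section 14 and the addendum show none. The tailored laboratory summaries in section 9.10 cover only platelets and prolactin, and the prolactin ones are not split by age or sex.

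**2. How much does pooling dilute a rise confined to prepubertal children?** Let f be their share of an arm and d the true active-placebo difference in change among them, with no difference in other subjects.

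- Pooled difference in mean change = f × d.
- With f assumed at 0.2, 0.3 and 0.4, this is 0.2d, 0.3d and 0.4d.

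To set this against noise, take n = 79 per arm (section 4.2) and d = 1 SD of the children's own change. Let the change in all other subjects have r times that SD. Apart from 79, every input is an assumption.

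- Children alone: z = √(n f / 2)
- Pooled: z = f √(n/2) / √(f + (1 − f) r²)

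For f = 0.2 and r = 1: children √(79 × 0.2 / 2) = √7.9 = 2.81; pooled 0.2 × √39.5 = 1.26. With r = 4, the pooled value is 1.26 / √(0.2 + 0.8 × 16) = 1.26 / 3.61 = 0.35.

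| f | children alone | pooled, r = 1 | pooled, r = 2 | pooled, r = 4 |
|---|---|---|---|---|
| 0.2 | 2.81 | 1.26 | 0.68 | 0.35 |
| 0.3 | 3.44 | 1.89 | 1.07 | 0.56 |
| 0.4 | 3.97 | 2.51 | 1.50 | 0.79 |

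The signal is weaker in every row, but it does not vanish in all of them. These tables are descriptive and no test is planned, so z only expresses signal against noise.

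**3. What can be read from Tanner counts by visit?** Suppose the same children are staged at both visits and none regresses. Then the number at stage k or above at Visit 12, minus the same number at Visit 3, is the number who crossed into k. Example: I = 10, II = 10 at Visit 3, and I = 6, II = 10, III = 4 at Visit 12.

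- At II or above: 14 − 10 = 4 crossed.
- At III or above: 4 − 0 = 4 crossed.

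Net progression is therefore readable from complete data. It fails when Visit 12 stages are missing. If four of the ten stage I children have no Visit 12 staging and nobody moves, the share at II or above goes from 10/20 = 50% to 10/16 = 62.5%. Nor do the counts show which child moved, or at what exact age.

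**The case against.** A reader might infer that early or faster puberty on drug could not be seen at all in the planned output. The documents do not support that:

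- The hormone shift tables are within-subject. A child moving from normal to above normal is counted whatever the pooled mean does.
- Tanner counts are already split by sex and three age bands at both visits, and with complete data they give net progression.
- Section 6.6.1 adds medians, quartiles, minimum and maximum to the mean and SD.
- Hormone and Tanner values are listed by subject, and section 9.10 promises a listing of markedly abnormal results.
- Clinically significant laboratory and examination findings are reported as adverse events, which are tabulated by age and by sex.

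It is also fair to say that puberty is not a named safety objective, that Part 1 treatment lasts 14 weeks, and that longer-term safety belongs to a separate Part 2 SAP. Table layouts sit in shells that are not shown. Whether the laboratory's limits are age- and sex-specific may be settled in laboratory documentation, so the SAP's silence on it is not itself an error.

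Most of this stands and sets the size of the point, but it does not remove it. The shift tables pool ages and sexes as well. Listings leave the comparison of arms to reading by eye. The index names extreme-value listings only for hematology, biochemistry and urinalysis, although section 9.10 promises them for each parameter. The adverse-event route depends on someone having recognised and reported the event.

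**Conclusion.** The point holds as one of poor fit between summary and purpose. The hormone tables pool both sexes and ages 2 to 35, and Tanner stage has no within-subject shift, so the planned summaries are poorly suited to detecting early or accelerated puberty. Partial cover exists through the shift tables, the listings and the adverse-event tables by age and sex.

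The size depends on the share of prepubertal children, which the SAP does not give. At an assumed 20-40% of an arm, a rise confined to them shows at 0.2-0.4 of its size in the pooled mean. The loss relative to noise depends further on the assumed SD ratio and should be taken as illustration only. The claim that such a rise would be reported as no change does not follow, because the mean is diluted rather than erased and other outputs remain. This is an inexpensive improvement to a safety presentation and does not touch the efficacy conclusions.

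**What to change.** In section 9.10, state that LH, FSH, testosterone, estradiol, GH and IGF-1 are summarised and shifted by treatment group, sex and the age groups already in use (2 to under 6, 6 to under 12, 12 to under 18, 18 to 35 years). Collapse bands where cells are very small, and amend Tables 14.3.4.4.1.x and 14.3.4.4.2.x to match. Section 14 rules out subset analyses for Cohort B because of its size, so there the split can be limited to what the numbers allow. A sentence saying whether the normal limits are age- and sex-specific would make the shift tables interpretable.

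In section 9.9, keep the visit counts and add a Visit 3 to Visit 12 Tanner shift table by treatment group, sex and existing age band, in subjects staged at both visits.

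No new data are needed. The cost is more pages and small cells: four age groups × two sexes × three arms = 24 cells, so about 250 randomised subjects average roughly 10 per cell before missing values. Means and SDs in such cells will be noisy, which is why collapsing should be allowed.
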